15. PROTOCOL AMENDMENT

The Investigator may recommend changes to the protocol. The sponsor will decide if an amendment to the original protocol is warranted. Protocol modifications that impact on study participant safety or the validity of the study will be reviewed and approved by the Ethics Committee prior to implementation.

It is the responsibility of the Investigator to submit the amendment to the Ethics Committee for their approval; written approval must be obtained and a copy provided to the Sponsor. The Sponsor is responsible for determining whether or not the local regulatory authority

must be notified of the protocol change. Completed and signed protocol amendments will be circulated to all those who were on the circulation list for the original protocol.

16. PUBLICATIONS

All information and data regarding the IP obtained in connection with the conduct of this study are considered confidential. Accordingly, the sponsor retains the right to review manuscripts, abstracts, and presentation material related to this protocol and its amendments/addenda prior to presentation or submission to a journal. This review will not restrict publication of facts or opinions formulated by the investigator.

17. RETENTION OF RECORDS AND ARCHIVING

All source documents, eCRFs and study documentation will be kept by the Investigator for the appropriate retention period as stipulated by local regulations and ICH-GCP.

19. APPENDICES

19.1. Appendix 1: Standard Cholesterol Lowering Diet

DIET

1. Consume a dietary pattern that emphasizes intake of vegetables, fruits, and whole grains; includes low-fat dairy products, poultry, fish, legumes, nontropical vegetable oils and nuts; and limits intake of sweets, sugar-sweetened beverages and red meats.
 - a. Adapt this dietary pattern to appropriate calorie requirements, personal and cultural food preferences, and nutrition therapy for other medical conditions (including diabetes mellitus).
 - b. Achieve this pattern by following plans such as the DASH dietary pattern, the USDA Food Pattern, or the AHA Diet.
2. Aim for a dietary pattern that achieves 5% to 6% of calories from saturated fat.
3. Reduce percent of calories from saturated fat.
4. Reduce percent of calories from *trans* fat.

*Refer to 2013 Blood Cholesterol Guideline (17, 18)

19.2. Appendix 2. Schedule of visits

Procedure/Visit	Screening Period (V1)	Randomization Baseline Visit (V2)	Visit 3 (V3)	End of Treatment Visit (V4)	Safety Follow-up Visit (V5) (telephone)
	Week -1 Up to 7 days	Week 0	Week 6 (± 5 days)	Week 12 (± 5 days)	Week 14 (± 5 days)
Informed consent form	X				
Inclusion & Exclusion criteria	X	X			
Medical History	X	X			
Demographics	X				
Physical examination	X			X	
Vital signs (blood pressure, pulse)	X	X	X	X	
Height	X				
Weight	X			X	
Dietary counselling including alcohol consumption, and timing of statin vs. IP intake	X	X	X		
Check compliance on statin and IP			X	X	
12-Lead ECG	X			X	
Hematology	X	X	X	X	
AST, ALT, Creatinine	X	X	X	X	
Bilirubin	X				
LDH, CPK		X	X	X	
TG, TC, LDL-C, HDL-C	X	X	X	X	
LDL-C (direct-measured), VLDL-C, apo-B, Lp(a), non-HDL-C, small low-density lipoprotein (LDL) subclass particle concentration		X	X	X	
HbA1c, Insulin, Glucose and hsCRP		X		X	
Concomitant medication	X	X	X	X	
Pregnancy test*	X*	X*			
Randomization		X			
IP dispensing		X	X		
Adverse Events	X**	X**	X**	X**	X**

*Female patients of childbearing potential will have a urine pregnancy test performed at the screening visit and at randomization (visit 2)

**Serious Adverse Events (SAEs) are captured from the time of consent through to week 14 safety Follow up phone call. AEs are captured between the time of randomization up to the last dose IP taken.

19.3. Appendix 3. Clinical Laboratory Parameters

Screening (Visit 1): The following screening laboratory assessments are to be performed during the screening period for the determination of study eligibility and the patient's current medical state at the time of study entry:

Determinations		
Hematology	RBC	
	Hemoglobin	
	Hematocrit	
	WBC	
	Platelet Count	
	Differential (to be performed only if WBC is abnormal)	Neutrophils
		Lymphocytes
		Monocytes
		Eosinophils
		Basophils
Biochemistry	AST	
	ALT	
	Bilirubin	
	Creatinine	
Lipids	Triglycerides	
	Total cholesterol	
	LDL-Cholesterol	
	HDL-Cholesterol	
Urine (only for females of childbearing potential)	human chorionic gonadotropin (hCG) urine pregnancy test	

Baseline and Treatment Period (Visits 2, 3, and 4)

Determinations		
Hematology	RBC	
	Hemoglobin	
	Hematocrit	
	WBC	
	Platelet Count	
	Differential (to be performed only if WBC is abnormal)	Neutrophils
		Lymphocytes
		Monocytes
		Eosinophils
		Basophils
Biochemistry	AST	
	ALT	
	LDH	
	CPK	
	Creatinine	
	Glucose (fasting) (at visit 2 and 4 only)	
	Insulin (fasting) (at visit 2 and 4 only)	
	HbA1c (at visit 2 and 4 only)	
	hs-CRP (at visit 2 and 4 only)	
Lipids / Other	Triglycerides	
	Total cholesterol	
	LDL-Cholesterol (direct-measured)	
	HDL-Cholesterol	
	VLDL Cholesterol	
	Apolipoprotein B (apo B)	
	Lipoprotein (a) [Lp(a)]	
	Non-HDL-C	
	small low-density lipoprotein (LDL) subclass particle concentration	

Urine (only for
females of
childbearing
potential)

human chorionic gonadotropin (hCG) urine pregnancy test
(Visit 2 only)

Female patients of childbearing potential will have a urine pregnancy test performed at the screening visit and at randomization (visit 2).

1 INTRODUCTION

The purpose of this statistical analysis plan (SAP) is to present the statistical methodology that will be used for the final analysis of CEAPRO Inc. protocol PROJ1601. This plan also provides a description of the tables, figures and listings that will be included in the final statistical report. It is based on the protocol version 2.1 dated 23JAN2020 and on the annotated case report form (CRF) version 2.0. In case of differences in terms of descriptions or explanations between the SAP and the clinical protocol, the SAP will supersede the protocol. Any deviation to this SAP would be reported in the statistical report.

2 STUDY DESCRIPTION

2.1 Study Design

This is a Phase 2, double-blind, randomized, multicenter, 12-week comparative study of beta-glucan versus placebo, in subjects with an elevated LDL-C $>3.37\text{mmol/L}$ (130 mg/dL) treated with a stable dose of statin for at least 6 weeks or not treated with a statin.

Following signature of informed consent, approximately 264 subjects (66 subjects per beta-glucan treatment group and 22 subjects per matching placebo group) meeting all inclusion criteria and no exclusion criteria will be randomized to receive one of the three doses of beta-glucan (1.5 g, 3 g or 6 g daily) TID or a matching placebo.

The subjects will be assigned to the three different doses of beta-glucan or placebo in a tiered fashion as follows:

- The first set of 88 subjects randomized will receive either 1.5 g beta-glucan (1 tablet of 500 mg TID) or a matching placebo in a 3:1 ratio,
- The next set of 88 subjects randomized will receive either 3 g of beta-glucan (2 tablets of 500 mg TID) or a matching placebo in a 3:1 ratio,
- The last set of 88 subjects randomized will receive either 6 g of beta-glucan (4 tablets of 500 mg TID) or a matching placebo in a 3:1 ratio.

The duration of treatment is twelve weeks with beta-glucan 1.5 g, beta-glucan 3 g, beta-glucan 6 g (total daily dose) or matching placebo. Each subject is expected to participate for about 15 weeks (up to 1 week of screening, 12-weeks of treatment and follow-up call 2 weeks after last dose taken).

[figure not shown]
[figure not shown]
[figure not shown]
At baseline Visit (Week 0), the subjects should be already on a standard cholesterol lowering diet (American Heart Association Guidelines) and they should maintain it throughout the study. Subjects are encouraged to pursue a healthy lifestyle. The subjects must abstain from/minimize alcohol (EtOH) intake and keep stable any other variables that may alter serum lipid levels (e.g., strenuous exercise, weight loss programs, drugs including over the counter preparations that may alter serum lipid levels).

During the treatment period, subjects will return to the study site at Visit 3 (Week 6) and at the End of Treatment Visit (Week 12) for laboratory tests and clinical assessments, including for Adverse Events (AEs), dietary guidance and IP compliance. At the Safety Follow-up Visit (Week 14), subjects will be contacted via telephone for an assessment of Adverse Events (AEs). Time window for the Visit 3 (Week 6), Final Visit (Week 12) and Safety Follow-up Visit is ± 5 days.

[figure not shown]
Laboratory tests and clinical assessments will be performed as noted in the schedule of visits (Appendix 1).

Safety and tolerability assessment will include AEs, hematology, biochemistry, physical examination, vital signs and electrocardiogram (ECG).

The study design is presented in the following figure.

* Subjects treated or not with a statin at baseline

W-1 (up to -7 day)

W0

W6 (\pm 5 days)

W12 (\pm 5 days)

W14 (\pm 5 days)

2.2 Study Objectives

The overall aim of this study is to evaluate the effects of beta-glucan (1.5 g, 3 g or 6 g daily) administered three times a day (TID) in divided doses compared to placebo on heart disease lipid risk factors.

The primary objective is to evaluate the effects of beta-glucan on the direct-measured Low-Density Lipoprotein Cholesterol (LDL-C) level compared to placebo after 12 weeks of treatment in subjects with LDL-C > 3.37 mmol/L (130 mg/dL).

The secondary objectives are to evaluate:

- The effects of beta-glucan on Total Cholesterol (TC), small LDL-C subclass particle concentration, high sensitivity C-reactive protein (hsCRP), non-High Density Lipoprotein Cholesterol (HDL-C), Apolipoprotein B (apo B) and Very Low Density Lipoprotein Cholesterol (VLDL-C) levels compared to placebo after 12 weeks of treatment.
- The safety profile of beta-glucan.

The exploratory objectives are to evaluate the effects of beta-glucan on HDL-C, Triglyceride (TG), Lipoprotein a (Lp(a)) and glycated hemoglobin (HbA1c) levels compared to placebo after 12 weeks of treatment.

3 DATASETS ANALYZED

Subjects who were not eligible for randomization but who have been erroneously randomized into the study will be excluded from all datasets analyzed, if they did not take study medication. All populations of analysis will be approved by the sponsor prior to unblinding.

3.1 Intent-To-Treat (ITT) Population

All patients randomized will be included in the ITT population (i.e. subjects having a randomization number on the Randomization Form of the electronic case report form (eCRF)). In the ITT population, subjects allocated to a treatment group by randomization will be followed up, assessed and analyzed as members of that group irrespective of their compliance to the planned course of treatment.

3.2 Per-Protocol Population

The per-protocol population will include all subjects randomized, excluding subjects who were not compliant to IP and who had major protocol deviation. Subjects will be assigned to treatment groups as randomized for analysis purposes. Specific requirements are:

- Compliance of at least 80%. The compliance will be taken from the Drug Accountability Form of the eCRF.
- Absence of any major protocol deviations that could affect the primary endpoint. Those major protocol deviations are defined as:
 - “Incorrect investigational product kit administrated to subject” on Protocol Deviation Form of the eCRF

- “Subject received another investigational product” on Protocol Deviation Form of the eCRF
- Inclusion criteria “Subjects with hyperlipidemia treated with stable dose of statin for at least 6 weeks; either atorvastatin (10 mg to 20 mg daily) or equivalent dose of another statin at the time of informed consent and with LDL-C level >3.37 mmol/L (130 mg/dL) in fasting conditions at screening.” not met on Inclusion/Exclusion Criteria Form of the eCRF version previous 2.1.
- Inclusion criteria “Subjects with hyperlipidemia with LDL-C level >3.37 mmol/L (130 mg/dL) in fasting conditions at screening, treated with a stable dose of statin for at least 6 weeks or not treated with a statin at the time of informed consent.” not met on Inclusion/Exclusion Criteria Form of the eCRF version 2.1.
- Any other protocol deviations considered as major as per the sponsor.

3.3 Safety Population

The safety population will include all randomized subjects who received at least one dose of IP (i.e. subjects with at least one non missing Investigational Product treatment period start date (variable EXSTDAT or a comment indicating unknown date of first dose) on Investigational Product Use Form of the eCRF). Subjects will be assigned to treatment groups as per actual treatment received for analysis purposes.

4 EFFICACY ENDPOINTS

4.1 Primary Efficacy Endpoint

The primary efficacy endpoint will be the change from Week 0 to Week 12 in direct-measured LDL-C.

4.2 Secondary Efficacy Endpoints

The secondary efficacy endpoints will be the changes from Week 0 to Week 12 in:

- TC
- non-HDL-C
- small LDL subclass particle concentration
- hsCRP
- VLDL-C
- Apo B

4.3 Exploratory Endpoints

Exploratory endpoints will include changes from Week 0 to Week 12 in:

- HDL-C
- TG
- Lp(a)
- HbA1c

5 SAFETY PARAMETERS

Safety will be assessed by adverse events (AEs) and serious adverse events (SAEs), physical examination results, vital signs, ECG and laboratory parameters (hematology, biochemistry).

5.1 Adverse Events

As per Natural Health Products Regulations SOR/2003-196, an AE is any adverse occurrence in the health of a clinical trial subject who is administered a natural health product that may or may not be caused by the administration of the natural health product, and includes an adverse reaction, a serious adverse reaction and a serious unexpected adverse reaction.

Exacerbation of a chronic or intermittent pre-existing condition including either an increase in frequency and/or intensity of the condition is to be reported as AE. Signs, symptoms, or the clinical sequelae of a suspected overdose of either IP or a concurrent medication are to be reported as AEs.

Medical or surgical procedures (e.g. endoscopy, appendectomy) are not to be reported as AEs; the medical condition that leads to the procedure is an AE. For each adverse event, start and stop dates, action taken, outcome, intensity and relationship to IP (causality) must be documented by the investigator. If an AE changes in frequency or intensity during a study, an update of the event must be made on the eCRF.

Treatment-emergent adverse events will be defined as adverse events with a start date on or after the first dose of study product (which will be derived as the earliest date of variable EXSTDAT on Investigational Product Use Form of the eCRF).

5.2 Serious Adverse Events

A serious adverse event is a noxious and unintended response to a natural health product that occurs at any dose and that requires in-patient hospitalization or prolongation of existing hospitalization that causes congenital malformation, results in persistent or significant disability or incapacity, is life-threatening or results in death.

SAEs will be collected from the time of consent through to 2 weeks after the last dose of study product.

5.3 Physical Examination

Physical examinations will include examination of the following body systems: general appearance, skin (including hair and nails), EENT (ears, eyes, nose, throat), neck/thyroid, chest/lungs, cardiovascular, gastrointestinal, genito-urinary (optional), neurological, lymphatic and musculoskeletal systems. Height and body weight will also be measured and recorded at Screening, and weight at the Week 12.

Any new clinically significant finding identified upon physical examination that meets the definition of an AE or SAE must be documented as such.

5.4 Vital Signs

Blood pressure and pulse will be recorded after at least 5-minute rest in the sitting position. Two measurements should be made for each blood pressure measurement and the average recorded. Vital sign checks will be performed at Screening, Baseline, Week 6 and Week 12.

5.5 Electrocardiogram

All ECGs will be obtained in the decubitus position following a 10-minute rest time. The following parameters PQ (PR), QRS, QT, RR, QTcB (calculated according to Bazett's formula) and the heart rate will be measured automatically and recorded in the eCRF at Screening and Week 12.

5.6 Laboratory Parameters

A full clinical laboratory profile including hematology, biochemistry, lipids and other analyses will be performed during the study. Laboratory data will be transferred electronically by the Dynacare central lab. Blood samples are to be collected at Screening, Baseline, Week 6, Week 12 and at some unscheduled visits if it is necessary to repeat testing following abnormal laboratory results. Here is the list of the collected laboratory assessment:

Screening (Visit 1): The following screening laboratory assessments are to be performed during the screening period for the determination of study eligibility and the patient's current medical state at the time of study entry:

| | Determinations | |
|---|--|---|
| Hematology | RBC | |
| | Hemoglobin | |
| | Hematocrit | |
| | WBC | |
| | Platelet Count | |
| | Differential (to be performed only if WBC is abnormal) | Neutrophils Lymphocytes Monocytes Eosinophils Basophils |
| Biochemistry | AST | |
| | ALT | |
| | Bilirubin | |
| | Creatinine | |
| | eGFR | |
| Lipids | Triglycerides | |
| | Total cholesterol | |
| | LDL-Cholesterol | |
| | HDL-Cholesterol | |
| Urine (only for females of childbearing potential) | Human chorionic gonadotropin (hCG) urine pregnancy test | |

Baseline and Treatment Period (Visits 2, 3, and 4)

| Determinations | | |
|---|--|---|
| Hematology | RBC | |
| | Hemoglobin | |
| | Hematocrit | |
| | WBC | |
| | Platelet Count | |
| | Differential (to be performed only if WBC is abnormal) | Neutrophils Lymphocytes Monocytes Eosinophils Basophils |
| Biochemistry | AST | |
| | ALT | |
| | LDH | |
| | CPK | |
| | Creatinine | |
| | eGFR | |
| | Glucose (fasting) (at visit 2 and 4 only) | |
| | Insulin (fasting) (at visit 2 and 4 only) | |
| | HbA1c (at visit 2 and 4 only) | |
| | hs-CRP (at visit 2 and 4 only) | |
| Lipids / Other | Triglycerides | |
| | Total cholesterol | |
| | LDL-Cholesterol (direct-measured) | |
| | HDL-Cholesterol | |
| | VLDL Cholesterol | |
| | Apolipoprotein B (apo B) | |
| | Lipoprotein (a) [Lp(a)] | |
| | Non-HDL-C | |
| | small low-density lipoprotein (LDL) subclass particle concentration | |
| Urine (only for females of childbearing potential) | Human chorionic gonadotropin (hCG) urine pregnancy test (Visit 2 only) | |

Female patients of childbearing potential will have a urine pregnancy test performed at the Screening visit and at Baseline.

6 STATISTICAL METHODOLOGY

6.1 Determination of Sample Size

Sample size computation was based on the change in LDL-cholesterol. Based on previous literature, we are expecting a mean decrease from baseline to follow-up in LDL-C of -0.30 mmol/L (11.6 mg/dl) in the placebo group and we are aiming to show that the addition of beta-glucan, either at 1.5 g, 3 g or 6 g, will further reduce LDL-C by -0.30 mmol/L, leading to an expected difference in change in LDL-C of 0.30

mmol/L between the placebo group and at least one of the active groups. The expected standard deviation of the change in LDL-C is 0.50 mmol/L (19.3 mg/dl). To reach a power of 80% in detecting this 0.30 mmol/L difference with a two-tailed significance level of 0.0167 (to account for three main comparisons (placebo vs. beta-glucan 1.5 g, placebo vs. beta-glucan 3 g and placebo vs. beta-glucan 6 g), 60 subjects per group were needed for a total of 240 subjects. To account for approximately 9% lost to follow-up, 264 subjects (66 subjects per treatment group) were randomized.

Sample size was calculated with nQuery + nTerim 2.0.

6.2 Statistical Considerations

This is a randomized, parallel study with four treatment groups (placebo, beta-glucan 1.5 g, beta-glucan 3 g and beta-glucan 6 g). The statistical analysis will focus on the comparisons of the three active groups vs. placebo.

Descriptive statistics of all study variables will be presented overall and broken down by treatment group. Number of observations, mean, standard deviation, median, minimum and maximum will be presented for continuous variables. Count and proportion will be displayed for categorical variables.

Basic assumptions of the proposed analyses will be checked and data transformation or other analyses could be done if appropriate. For example, as some endpoints are likely to be skewed (ex. triglycerides, hsCRP), log-transformation might be used, in which case descriptive statistics would also include geometric means.

Laboratory parameters will be assigned to visits based on number of days from randomization and not based on scheduled visit at which the measurement was made. The time windows that will be used to assign measurements to visits are given in Appendix 2.

Values entered as less than a specified value will be considered as the specified value divided by 2 (e.g. entered value <0.2 will be analyzed as 0.1). Values entered as BLQ (Below Limit of Quantification) will be considered as the limit of quantification divided by 2. Values entered as more than a specified value will be considered as the specified value.

All statistical tests will be two-sided. Tests involving the comparisons of the active groups vs. placebo for the primary endpoint will be conducted at the 0.0167 significance level. All other tests will be considered secondary or exploratory and will be conducted at the 0.05 significance level.

No interim analysis on efficacy endpoints is planned for this study.

Statistical analyses will be done using SAS version 9.4 or higher.

6.2.1 Handling of Missing Data

For efficacy laboratory endpoints, the screening value will be taken if the baseline value is missing.

In addition, the proposed statistical analysis will account for all available data and will not disregard subjects with missing data at either Week 6 or Week 12. However, in subjects who will only have a baseline measurement, the last observation carried forward approach will be used.

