6.3.6 Treatment Compliance

An overall compliance calculation will be performed using primarily the study administration intake recorded on the Drug Accountability Form of the eCRF or on the Investigational Product Use Form of the eCRF if information regarding study medication returned/lost is missing. Compliance for the whole study is derived as follows:

| | | |
|------------------------|-----------------------|---|
| | Pill counts (%) | $\frac{[\text{sum of caplets dispensed} - \text{sum of caplets returned} - \text{sum of caplets lost}] \times 100}{[\# \text{ caplets to take per day} \times (\text{date last scheduled visit} - \text{date rando})]}$ |
| Compliance overall (%) | Days on treatment (%) | 
If # of caplets dispensed ≠ missing AND If information regarding study medication returned is missing (i.e. # of caplets returned is missing and/or # of caplets lost is missing)
 $\frac{[\text{date of last dose} - \text{date of first dose}] \times 100}{[\text{date last scheduled visit} - \text{date rando}]}$ |
| | NA | 
If # of caplets dispensed = missing OR If last scheduled visit = baseline
 |

Where

- Cohort 1 (rando number 001 à 280): Number of tablets dispensed = 147 (# caplets per day = 3)
- Cohort 2 (rando number 281 à 563): Number of tablets dispensed = 294 (# caplets per day = 6)
- Cohort 3 (rando number 564 à 997): Number of tablets dispensed = 588 (# caplets per day = 12)

Compliance will also be categorized as follow: < 80%, [80%-120%] or >120% and summarized accordingly using frequencies and percentages, by treatment arm, for the subjects of the ITT population.

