6.4.1 Primary Analysis

The primary endpoint is the change from Week 0 to Week 12 in direct-measured LDL-C. The changes, as well as the LDL-C values at each study visit, will be summarized with descriptive statistics.

The primary endpoint will be compared between treatment groups using a repeated measures analysis of covariance (ANCOVA) model.. More specifically, the dependent variable will be the change from Week 0 in LDL-C (change calculated as post Week 0 level – Week 0 level) the model will include treatment group, time (Week 6 and Week 12) and treatment group x time interaction as well as the covariates of Week 0 value of LDL-C and Week 0 value of LDL-C x time interaction. An unstructured covariance structure will be

used to model the within-patient errors and the Kenward-Roger approximation will be used to estimate denominator degrees of freedom. Contrasts under this model will allow for the three main comparisons: placebo vs. beta-glucan 1.5 g, placebo vs. beta-glucan 3 g and placebo vs. beta-glucan 6 g. More specifically, the following hypotheses will be tested:

$$H_0: \Delta_{W12,\text{placebo}} = \Delta_{W12,1.5g} \quad \text{vs.} \quad H_1: \Delta_{W12,\text{placebo}} \neq \Delta_{W12,1.5g}$$

$$H_0: \Delta_{W12,\text{placebo}} = \Delta_{W12,3g} \quad \text{vs.} \quad H_1: \Delta_{W12,\text{placebo}} \neq \Delta_{W12,3g}$$

$$H_0: \Delta_{W12,\text{placebo}} = \Delta_{W12,6g} \quad \text{vs.} \quad H_1: \Delta_{W12,\text{placebo}} \neq \Delta_{W12,6g}$$

where $\Delta_{W12,\text{placebo}}$, $\Delta_{W12,1.5g}$, $\Delta_{W12,3g}$ and $\Delta_{W12,6g}$ are respectively the mean change from Week 0 to Week 12 in LDL-C in the placebo, beta-glucan 1.5 g, beta-glucan 3 g and beta-glucan 6 g group.

All sets of hypotheses will be tested at the 0.0167 significance level to maintain the overall type I error to 0.05 for the primary endpoint. These tests will be considered as the primary analysis of the study.

For illustrative purposes, changes within groups will be tested at the 0.05 significance level. Estimates of the changes within groups and of the between-group differences will also be presented along with 95% confidence intervals.

The same ANCOVA model will also allow for the examination of the change from Week 0 to Week 6 in LDL-C. In other words, the hypotheses described above will also be tested at Week 6 at the 0.05 significance level for illustrative purposes.

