Because the SAS procedure PROC MIXED will be used, subjects with missing data at a given study visit will not be excluded from the analysis.

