6.4.4 Sensitivity Analysis

6.4.4.1 Per-Protocol Analysis

The analysis of the primary endpoint described in section 6.4.1 will be repeated on the PP population. The tests will be conducted at the 0.05 significance level.

To better understand the impact of compliance, the same analysis will be repeated on a modified version of the PP population where the compliance criteria will be set to 70%. In other word, the analysis of the primary endpoint will be conducted in patients who had a compliance of at least 70% and no major protocol deviations that could affect the primary endpoint.

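### Carrying baseline forward for subjects with only a baseline value puts a change of exactly zero into the primary LDL-C model as if it had been measured

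*SAP*

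**What the plan says.** SAP 6.2.1 has two rules for missing post-baseline data. A subject missing Week 6 or Week 12, but not both, is analysed on the available data. The exception is that "in subjects who will only have a baseline measurement, the last observation carried forward approach will be used".

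In SAP 6.4.1, "the dependent variable will be the change from Week 0 in LDL-C", at Weeks 6 and 12. The model has treatment, time, their interaction, baseline and baseline by time, with an unstructured covariance. The section adds that, because PROC MIXED is used, "subjects with missing data at a given study visit will not be excluded from the analysis". Protocol 10.3.1 makes the same statement about PROC MIXED, and the protocol mentions neither last observation carried forward nor any other imputation. Where the documents differ, "the SAP will supersede the protocol" (SAP section 1).

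For the sample size (SAP 6.1), "we are expecting a mean decrease from baseline to follow-up in LDL-C of -0.30 mmol/L (11.6 mg/dl) in the placebo group", with a further 0.30 fall on active treatment, an SD of 0.50, and about 9% lost to follow-up.

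The planned sensitivity analyses (SAP 6.4.4) are a per-protocol analysis at 80% compliance, a modified version at 70%, and a dose-response regression.

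**The concern.** A carried-forward baseline minus baseline is 0. The model receives that value with the same standing as a laboratory result, and nothing in the standard error reflects that it was filled in. Every other missing visit is left to the likelihood under missing at random. The primary analysis therefore combines two different missing-data assumptions, and the one applied to baseline-only subjects disagrees with both means in the sample-size section.

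Two things are at stake. One is a diluted treatment estimate with some loss of power. The other is a contrast that shifts for reasons unrelated to the product if arms differ in how many subjects leave before any post-baseline draw. With the plan as written, a reader of the final report could not tell how much of the result came from filled values.

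**Working it through.** **Inputs from the documents.** Placebo change -0.30, active change -0.60, SD 0.50 mmol/L, two-sided alpha 0.0167, 60 evaluable and 66 randomised per arm, 9% loss (SAP 6.1). The placebo arm is pooled: 3 × 22 = 66 (SAP 2.1).

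**Not in the documents (assumed).** The share p of subjects with only a baseline value, taken as 0 to 9%. The 9% ceiling treats the whole planned loss as baseline-only.

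**The plan's own figure.** A two-sample t-test with difference 0.30, SD 0.50 and alpha 0.0167 has power 79.5% at 59 per arm and 80.3% at 60. Then 60/0.91 = 65.9, so 66 per arm and 264 in total. The stated sample size reproduces.

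**Effect on the contrast.** Write the contrast as placebo change minus active change, so that benefit is positive. Let pa and pp be the baseline-only shares on active and placebo, with missingness unrelated to outcome:

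contrast = (1-pa) × 0.60 - (1-pp) × 0.30

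With pa = pp = p this is 0.30(1-p). For any common placebo change it is (1-p) times the true difference, so a true null stays at zero.

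**Power, unadjusted t-test.** With the fill, the variance in an arm with mean change m is (1-p) × 0.25 + p(1-p) × m², with n = 66. Without it, the SD is 0.50 and n = 66(1-p). At p = 9% the arm SDs are 0.507 (active) and 0.485 (placebo). Power is 76.9% with the fill and 80.4% without. At p = 3% it is 82.1% and 83.2%.

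**Power, repeated-measures model by simulation.** 20,000 trials per scenario, four arms of 66. Assumptions: baseline SD 0.6, baseline-change correlation -0.3, Week 6-Week 12 correlation 0.6, equal means at both visits. A delta-method standard error with a t reference stood in for Kenward-Roger. Monte Carlo error is about 0.3 points for power and 0.0015 for family-wise error.

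| Baseline-only share | Contrast | Power with fill | Power without |
|---|---|---|---|
| 3% in all arms, plus 6% with Week 6 only | 0.291 | 84.0% | 85.5% |
| 9% in all arms | 0.273 | 80.0% | 84.8% |
| 9% active, 3% placebo | 0.256 (formula 0.255) | 71.7% | 84.7% |
| 3% active, 9% placebo | 0.309 | 89.4% | 84.7% |

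Baseline adjustment explains why these powers exceed the unadjusted ones.

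**Type I error.** With equal shares, family-wise error is 0.044 with and without the fill. With no drug effect and a placebo change of -0.30, the two unequal rows shift the contrast by 0.30 × (0.09 - 0.03) = 0.018, against active in the 9%/3% row and in its favour in the 3%/9% row. Per-comparison error becomes 0.020 and 0.019 (0.017 without the fill), and family-wise error 0.050 and 0.049 (0.044 without).

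**Dependence on the placebo change.** Subjects should already be on the diet at Week 0 (Protocol 3.1), so the placebo fall may be smaller than 0.30. For 3% active and 9% placebo, with a true difference of 0.30:

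| Placebo change | Contrast | Shift under the null |
|---|---|---|
| -0.30 | 0.309 | 0.018 |
| -0.15 | 0.300 | 0.009 |
| 0 | 0.291 | 0 |

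**Per subject.** Each filled active subject moves its contrast 0.60/66 = 0.009 mmol/L toward zero. Each filled placebo subject moves all three contrasts 0.30/66 = 0.0045 away from zero.

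**Do the planned analyses isolate the rule?** Compliance is set to NA under the condition "If last scheduled visit = baseline" (SAP 6.3.6). The per-protocol set requires "Compliance of at least 80%. The compliance will be taken from the Drug Accountability Form of the eCRF", and the modified set is "patients who had a compliance of at least 70% and no major protocol deviations that could affect the primary endpoint". Both probably drop most filled subjects, although the SAP does not say how NA is handled. Both also drop non-compliers and major deviators, so a difference from the ITT result could not be attributed to the fill. The SAP's list of tables has no count of filled subjects.

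**The case against.** The strongest case for the plan has four parts.

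- **It serves intention to treat.** In a change-from-baseline PROC MIXED a baseline-only subject has no outcome record, so without some fill that subject is in the ITT set by label only. The purpose is legitimate. It does not justify a fixed zero, since imputation retains these subjects under a stated assumption and carries its uncertainty.
- **Dilution is relative to the chosen estimand.** A subject never sampled after baseline may have taken little product. Placebo-based imputation gives such active subjects about -0.30, so the contrast becomes (1-pa) × 0.30, or 0.273 at 9%. With equal shares that equals the carried-forward result, so dilution alone is a weak complaint. What remains is that zeros are treated as data and that unequal shares shift the contrast even with no drug effect. Under placebo-based imputation they would not.
- **Few subjects are affected.** Any draw from Day 3 counts as Week 6 or Week 12 (SAP Appendix 2). Early leavers are encouraged to complete Visit 4 procedures (Protocol 6.11), and subjects who stop product stay in follow-up (Protocol 4.3, 5.5). Ineligible subjects randomised in error and never dosed are excluded (SAP section 3). This stands: the share should be below 9%.
- **A SAP may add detail.** Protocol 10.2 leaves full description to the SAP, and 10.3.1 does not address subjects with no post-baseline value. This also stands. The rule is an addition to the protocol's approach rather than a direct contradiction, and its absence from the protocol is not in itself a fault.

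**Conclusion.** The concern holds and should be fixed, but it does not threaten the trial's conclusions. With equal shares up to the planned 9% loss, the rule reduces the expected contrast by at most 9% of its value (0.300 to 0.273) and costs between 1.5 and 4.8 points of simulated power, or 1.1 to 3.5 points in the unadjusted calculation. It does not bias a true null. The larger figures (0.255 to 0.309, power from 71.7% to 89.4%) need unequal shares. Those are an assumption, because the documents give no arm-specific loss. In that setting the rule can act in either direction, so it cannot be defended as conservative. Family-wise error stays at about 0.05 or below in all of these scenarios. The simulated powers depend on the assumed correlations, while the contrast figures depend only on the planning means, the shares and missingness unrelated to outcome.

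Two smaller points belong to the same section. First, the sentence does not say whether it works per subject or per endpoint. If per endpoint, anyone without a Week 12 draw would receive a zero change for hsCRP and HbA1c, which are drawn only at Visits 2 and 4. Second, the screening fallback for a missing baseline cannot supply direct-measured LDL-C, which is not scheduled at screening.

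**What to change.** - Delete the carry-forward sentence from SAP 6.2.1, so that the primary model uses observed post-baseline values only, in line with Protocol 10.3.1. State that no fill applies to secondary or exploratory endpoints, including hsCRP and HbA1c.
- Report the number of subjects with only a baseline value, by arm.
- Add one multiple-imputation sensitivity analysis of the primary endpoint, for example placebo-based, that covers subjects with no post-baseline value.
- Limit the screening fallback to endpoints measured as the same variable at screening: TC, HDL-C and TG, plus non-HDL-C if it is calculated as TC minus HDL-C.

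The cost is one sentence deleted, about three added or edited, one table row and one imputation program. The primary model is unchanged. The trade-off is that baseline-only subjects then contribute no Week 12 value to the primary model, which rests on missing at random. They remain in the ITT set and in the imputation analysis.
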